PROTOCOL: An Open Label Trial of Aripiprazole in the Treatment of Conduct Disorder in Adolescents.

Rationale:

The use of atypical antipsychotics in children began in 1992 with several small case series with clozapine. Since that time, five other atypical agents, risperidone, olanzapine, quetiapine, ziprasidone and aripiprazole have been introduced into the US market. The newer atypical agents are not associated with agranulocytosis that has limited the usefulness of clozapine. Among the atypical antipsychotics, risperidone has remained the most extensively studied in children and adolescents, for a variety of problems, including Tourette's disorder, conduct disorder, schizophrenia, aggression, and pervasive development disorder. Risperidone has been shown to be an effective treatment in many of these disorders. However, weight gain, hyperprolactinemia, and extrapyramidal symptoms (EPS) are troublesome adverse effects more commonly associated with risperidone such that the drug's utility in this aged patient population is limited. We expect that the utility of aripiprazole in treating the pediatric population will not be limited by adverse effects like the other atypical antipsychotics.

Previous Work:

Several small studies have found risperidone to be more effective than placebo in treating children and adolescents with either aggression or conduct disorder. In a 10-week, randomized, double-blind study (n=20), risperidone was superior to placebo in reducing most measures of the Rating of Aggression Against People and/or Property Scale (RAAPP), when dosed at an average of 0.028mg/kg/day [range = 0.75-1.50 mg/day] (Findling et al 2000). The data also suggested that treatment with risperidone was associated with weight gain. The predicted weight gain from a repeated measures analysis for the risperidone group of 4.2 ± 0.7 kg was greater than the placebo group (p=0.003). There was no difference in the incidence of EPS at endpoint according to the Simpson-Angus EPS (SAEPS) rating scale.

Buitelaar et al (2001) assessed the efficacy of risperidone in the treatment of aggression. Thirty-eight adolescents were randomized to either risperidone or placebo in a double-blind fashion. The mean daily dose of risperidone at end of treatment (6 weeks) was 2.9mg [range = 1.5-4 mg]. Risperidone treatment produced improvement on the Clinical Global Impression-Severity (CGI-S) scale (LOCF, p<0.001) and the at-school Aberrant Behavior Checklist (ABC) overall and hyperactivity scales (p<0.05). In the risperidone group, following a 2-week washout following the 6-week trial worsening on all efficacy measures (CGI-S, Overt Aggression Scale-Modified (OAS-M), and the ABC. Weight gain was significant in the risperidone group (3.5% body weight increase, range – 1 to +6kg, p<0.05). Transient tiredness was also noted in 58% of drug-treated subjects, and was also the reason for dose reduction in five of the drug-treated subjects. Extrapyramidal Side Effect Rating Scale (ESRS) scores increased for Parkinsonism (cluster II) at endpoint compared to placebo (p<0.05).

Bellinghen et al (2001) compared risperidone (n=6) to placebo (n=7) in the treatment of behavioral disturbances in children and adolescents. Thirteen patients were enrolled in a 4-week double-blind, placebo-controlled study. Risperidone (mean dose = 0.05mg/kg; mean total dose = 1.2 mg/day) was more effective than placebo in improving ABC cluster scores for irritation and hyperactivity, the CGI scale. No significant differences in EPS symptoms or weight gain were seen between the treatment groups. The lack of any adverse effect differences is not surprising considering the low dose of risperidone and the small number of patients enrolled in the study.

Methods:

Dose and Schedule of Treatment: The proposed study will be a 6-week open label study evaluating aripiprazole in the treatment of 12 male post-pubertal adolescents (13-17 years, Tanner Stage 4) diagnosed with conduct disorder. The initial dose depending on the weight of the patient will be as follows: < 25 kg = 1 mg/d; 25-50 kg = 2 mg/d; 50-70 kg = 5 mg/d; > 70 kg = 10 mg/d (Data on File, 2003, Bristol-Myers Squibb). Thereafter the dose will be flexible based on response and tolerance.

Main outcome measures: The primary outcome efficacy measures will be the Rating of Aggression Against People and/or Property Scale (RAAPP) (Kemph et al 1993), Overt Aggression Scale-Modified (OAS-M) (Kay et al 1988), and Children’s Aggression Scale-Parent Version (CAS-P) (Halpern et al 2002) while the secondary outcome measure will be the CGI severity and improvement scale (NIMH, 1985a). Safety measures for extrapyramidal adverse effects will include the AIMS (NIMH, 1985b) for tardive dyskinesia, Barnes Akathisia Scale (Barnes 1989) (BAS) and the Simpson-Angus Scale (SAS) (Simpson and Angus 1970). The UKU (Lingjaerde et al 1987) will be used for monitoring non-motor adverse effects. Height, weight and body mass index measurements as well as initial and endpoint fasting blood sugars and lipids will assess the effect of weight change. Obtaining serum prolactin levels as well as screening for the sexual dysfunction adverse effects including galactorrhea, gynecomastia, menstrual irregularities and changes in libido will assess sexual dysfunction adverse effects. An initial and endpoint ECG will be obtained to monitor patients for any changes in the QT-corrected interval. A gamma-GT will be collected to monitor liver function.

Schedule of Events:

Procedure	screening (-7 to -28days)	baseline	week 1	week 2	week 4	week 6
History-Demographics	X					
Physical Exam	X					X
ECG	X					X
Vitals, Height, Weight, BMI	X	X	X	X	X	X
Urine Collection	X					X
Phlebotomy	X					X
Dispense Study Drug		X	X	X	X	X
Determine medication compliance			X	X	X	X

Laboratory Tests

fasting glucose	X					X
fasting lipid profile:						
total cholesterol	X					X
HDL-cholesterol	X					X
LDL-cholesterol	X					X
Triglycerides	X					X
Prolactin	X					X
Gamma GT	X					X
CBC	X					X
Urine Drugs of Abuse Screen	X					X

Psychiatric Rating Scales

RAAPP		X	X	X	X	X
CAS-P		X	X	X	X	X
OAS		X	X	X	X	X
CGI-S		X	X	X	X	X
CGI-I			X	X	X	X

Side Effect Rating Scales

AIMS		X	X	X	X	X
SAS		X	X	X	X	X
UKU		X	X	X	X	X
BAS		X	X	X	X	X

References:

Buitelaar JK, van der Gaag, R, Cohen-Kettenis P, et al (2001). A randomized controlled trial of risperidone in the treatment of aggression in hospitalized adolescents with subaverage cognitive abilities. *J Clin Psychiatry* 62:239-48.

Barnes TRE (1989). A rating scale for drug-induced akathisia. *Br j Psychiatry* 154:672-6.

Data on File, 2003, Bristol-Myers Squibb Company, Princeton, NJ 08536

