All statistical analyses were conducted using InStat 3.1a (GraphPad Software, La Jolla, CA). A modified intent-to-treat (ITT) population was used for analyses. For each outcome variable, the modified ITT population included all subjects with at least one post-baseline psychometric measurement (subjects received at least one week of aripiprazole). Demographic data is presented as means and standard deviations while bivariant data were contrasted using paired-t tests. A repeated measure analysis of variance (ANOVA) model was used to assess the changes in the psychometric tests. In cases where a subject did not complete the entire 6-week trial, the last available observation was carried forward (LOCF) and used for statistical comparisons. A repeated measure analysis of variance was used to assess the changes in the psychometric tests. For determining significance of statistical tests \langle was set at 0.05.

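### Three unranked primary scales share one 0.05 level with no success rule; if any one may count, error for no change over time is about 9 to 14% under sphericity

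*Protocol*

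**What the plan says.** The protocol (Methods, Main outcome measures) begins "The primary outcome efficacy measures will be the Rating of Aggression Against People and/or Property Scale (RAAPP", continues the list with OAS-M and CAS-P, and makes CGI the only secondary efficacy measure. It does not rank the three primaries. The Schedule of Events rates each at baseline and weeks 1, 2, 4 and 6. Dose and Schedule of Treatment describes a "6-week open label study evaluating aripiprazole in the treatment of 12 male post-pubertal adolescents".

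The SAP is one paragraph. On the scales it says "A repeated measure analysis of variance (ANOVA) model was used to assess the changes in the psychometric tests". Its last sentence, which begins "For determining significance of statistical tests", sets one level, 0.05. The sentence on demographics adds that "bivariant data were contrasted using paired-t tests". For patients who stop early, "the last available observation was carried forward (LOCF" is the rule. The population is set scale by scale: "For each outcome variable, the modified ITT population included all subjects with at least one post-baseline psychometric measurement".

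Neither document says how many primary scales must be significant, in what order they are read, whether the level is shared, which direction of change counts, or whether the ANOVA is corrected for non-sphericity.

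**The concern.** The protocol separates primary from secondary outcomes, but leaves three scales on the primary side and does not define a positive primary result. Each scale gets its own test at 0.05. Nothing in the text stops one significant scale, picked once the data are seen, from being presented as the primary finding. On that reading the overall error exceeds the stated 0.05.

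A second gap sits beside the first. An uncorrected repeated measures F test is too liberal when ratings close in time correlate more than ratings far apart. It needs its own remedy, because a multiplicity rule alone does not repair it. The omnibus F is also non-directional, so a significant result need not mean less aggression.

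**Working it through.** The documents give no power or familywise error figure to reproduce.

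**Inputs from the documents.** 12 patients; 5 rating occasions; 3 primary scales; level 0.05; ANOVA with 5 - 1 = 4 and 4 x 11 = 44 degrees of freedom; no correction stated.

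**Assumptions, none in the documents.** Normal scores; between-scale correlation 0, 0.5, 0.8 or 0.9; visit correlations either equal at 0.5 (sphericity holds) or decaying per week. Near-zero between-scale correlation is unlikely.

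**Bound by hand.** Three independent tests: 1 - (1 - 0.05)^3 = 14.3%. At correlation 1 the three tests are one test: 5%.

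**Simulation with no change over time.** Success means any scale with uncorrected F p < 0.05. There were 100,000 trials per cell for the equal and 0.85 rows and 40,000 for the others, so simulation error is about 0.1 to 0.2 percentage points.

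| Visit correlation | One scale | Any one: corr. 0 | 0.5 | 0.8 | 0.9 |
|---|---|---|---|---|---|
| Equal | 5.0% | 14.4% | 13.1% | 10.3% | 8.7% |
| 0.5 per week | 5.7 to 6.0% | 16.7% | 14.6% | 11.9% | 10.0% |
| 0.85 per week | 7.9% | 21.7% | 19.4% | 15.4% | 13.2% |
| 0.95 per week | 8.4 to 8.9% | 23.6% | 20.7% | 16.3% | 14.3% |

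Under sphericity the any-one error falls further, to 7.8% at between-scale correlation 0.95. The one-scale column isolates the effect of the uncorrected F; the rest of the excess comes from having three scales.

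**Direction.** Significant with week 6 below baseline, same order of correlations: equal 7.4, 6.8, 5.3, 4.5% against 2.5% for one scale; 0.85 per week 11.4, 9.8, 7.7, 6.6% against 3.9%.

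**Other success rules.**
- All three required: 0 to 2.0% (equal) or 0.1 to 3.6% (0.85 per week) when nothing changes. With valid tests this rule cannot exceed 5%.
- Two of three required: 0.7 to 4.4% (equal) or 1.8 to 6.9% (0.85 per week) when nothing changes. If one scale truly changes strongly, only one false result among the other two is needed. For independent tests that is 1 - 0.95^2 = 9.75%; simulation under sphericity gives about 7 to 10%.

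**Which remedy holds 5%** (any rejection, nothing changing, correlations 0, 0.5, 0.8, 0.9):

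| Holm applied to | Equal | 0.85 per week |
|---|---|---|
| Uncorrected F | 5.0, 4.7, 3.9, 3.1% | 11.1, 10.1, 8.2, 6.9% |
| Greenhouse-Geisser F | 2.3, 2.2, 1.9, 1.5% | 4.7, 4.4, 3.6, 3.0% |
| Paired t, baseline to week 6 | 4.9, 4.6, 3.8, 3.2% | 4.8, 4.5, 3.8, 3.2% |

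**Dropout check.** With 10% stopping at each visit after week 1 (1 - 0.9^3 = 27% in all), unrelated to score, and LOCF, the any-one error at correlations 0, 0.8, 0.9 is 14.6, 10.5, 8.8% (equal) or 21.2, 15.3, 12.9% (0.85 per week). Little changes.

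**The case against.** The strongest reply is that the harm rests on a reading the documents do not state. All three scales are primary, so a report of one alone would omit two named primaries. That is selective reporting that the plan fails to prevent, rather than something it instructs. This stands, and the error rates are conditional on that reading.

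Next, this is a small uncontrolled pilot with no stated success claim. Expectancy and regression to the mean can move all three scales together, and no adjustment deals with either. This also stands and limits the weight of the point. It does not remove it, since the plan labels outcomes primary and sets a significance threshold.

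A reader might infer that three scales alone push error to 22% or more. The documents do not support that. The figure needs uncorrelated scales and an assumed decay of visit correlations, and it mixes multiplicity with the uncorrected F. Nor are these rates of false attribution to the drug, because the null is only no change over time. Calling the ANOVA error two-sided would also be wrong, since an omnibus F has no direction and the SAP states no sidedness.

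**Conclusion.** The omission is certain: three unranked primaries, one 0.05 level, and no order, adjustment, direction or success rule. Its size is conditional. If any one scale may count, non-directional error for no change over time is about 9 to 14% under sphericity, for between-scale correlation 0.9 to 0, with the lower part more plausible. Significance in the direction of improvement is about 4.5 to 7.4% against 2.5%. The missing sphericity correction is a separate fault. It gives about 6 to 9% per scale under the decay patterns tried and raises any-one error to about 10 to 24% (13 to 22% at 0.85 per week).

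Requiring all three scales would hold 5% with valid tests. Requiring two would do so only if no scale truly changes. The text does not show which rule was meant. The sponsor should correct this, but it ranks below the lack of a control group.

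**What to change.** **If no data have been seen.** Name one score per scale; Previous Work itself refers to several RAAPP measures. Then either (a) name one primary scale or a fixed testing order, or (b) apply Holm at an overall 0.05: smallest p-value against 0.05/3 = 0.0167, next against 0.025, largest against 0.05, stopping at the first failure. Take the p-values from either the Greenhouse-Geisser corrected ANOVA or the baseline to week 6 paired t test (LOCF), chosen in advance. Count a scale as positive only if its week 6 mean shows less aggression than baseline, and report all three together.

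**If results are already known.** The past tense of "All statistical analyses were conducted using InStat 3.1a" suggests this but does not prove it. Keep the stated ANOVA, add the Greenhouse-Geisser correction, and report all three scales together with the scores used and with unadjusted and Holm-adjusted p-values. Show paired t tests only as supportive, since swapping the test now would add analytic freedom. State that no success rule was preset. Alternatively, label all three results exploratory and make no 5% error claim.

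**Cost.** A few sentences and arithmetic on three p-values, with no extra patients or data. Option (a) loses no power on the leading scale. Under (b), for assumed true changes of 0.5, 0.8 and 1.2 SD of the change, paired t power at the strictest Holm step falls from 35% to 19%, 71% to 51% and 97% to 89% with 12 patients. With 10 analysed it falls from 29% to 15%, 62% to 40% and 92% to 78%. If all three scales share a 0.8 SD effect (correlation 0.8, equal visit correlations), average per-scale power under Holm is 59% for paired t. For Greenhouse-Geisser ANOVA at 0.8 SD it is 43% (equal) or 56% (0.85 per week) if change is linear, and 56% or 75% if the full change is present from week 1. The paired t test would largely miss an early effect that fades by week 6.

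### CGI-I has no baseline rating, so the SAP's repeated-measures ANOVA, if applied to it, compares post-treatment visits with each other and is not anchored to no change

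*Protocol*

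**What the plan says.** Protocol, Methods, Main outcome measures: RAAPP, OAS-M and CAS-P are primary, "while the secondary outcome measure will be the CGI severity and improvement scale". In the Schedule of Events, the three primary scales and CGI-S are marked at baseline and at weeks 1, 2, 4 and 6. CGI-I is marked at weeks 1, 2, 4 and 6 only. That is not a scheduling slip: an improvement scale is itself a rating of change, so there is nothing to rate at baseline.

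The SAP names no individual scale. On the test it says "A repeated measure analysis of variance (ANOVA) model was used to assess the changes in the psychometric tests", and separately that "bivariant data were contrasted using paired-t tests". On the population: "For each outcome variable, the modified ITT population included all subjects with at least one post-baseline psychometric measurement". On missing visits: "the last available observation was carried forward (LOCF) and used for statistical comparisons". Alpha "was set at 0.05", with sidedness not stated. It gives no reference score, responder definition or one-sample test for CGI-I.

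**The concern.** For a scale with a baseline, a repeated-measures ANOVA across visits includes the pre-treatment level, so a difference between visits can reflect change from baseline. CGI-I has no such level. The question of interest is where its ratings sit relative to no change, and a comparison of weeks 1, 2, 4 and 6 with each other does not ask that. Improvement reached by week 1 and then held would tend to give a null result. Early worsening that recovers only to no change would tend to give a significant one. The second is a correct rejection of equal visit means, but wrong if read as improvement.

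The paired t-test does not fill the gap. There is no baseline CGI-I to pair with, and pairing week 1 with week 6 has the same lack of anchor.

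At stake is the reading of one part of one secondary outcome.

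**Working it through.** **Inputs from the documents.** Planned n = 12, single arm, open label (Protocol, Methods). CGI-I at 4 visits and CGI-S at 5 (Schedule of Events). Repeated-measures ANOVA, LOCF and alpha 0.05 (SAP). The plan gives no power, effect size or SD, so there is no figure of its own to reproduce.

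**Step 1: what the F test compares.** For n patients and k visits,

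F = [n Σⱼ(Ȳ.ⱼ − Ȳ..)² / (k − 1)] / [Σᵢⱼ(Yᵢⱼ − Ȳᵢ. − Ȳ.ⱼ + Ȳ..)² / ((n − 1)(k − 1))].

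- CGI-I: k = 4, df = 3 and 11 × 3 = 33. The null is equal means at weeks 1, 2, 4 and 6.
- A scale with a baseline: k = 5, df = 4 and 11 × 4 = 44. The null includes the baseline mean.

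If a constant c is added to every rating, each mean in the formula also rises by c and every difference is unchanged, so F is unchanged. On a simulated 12 × 4 data set, subtracting 2 points from every rating left p at 0.2926. This result needs no assumption about the scale: F carries no information on the distance from no change.

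**Step 2: how much it could matter.** Assumptions, none in the documents: 7-point scale with 4 = no change and lower = better, SD 1, equal between-visit correlation 0.6, means linear over the four visits, normal ratings rounded and clipped to 1–7, two-sided 0.05. There were 10,000 simulated trials per row. Entries are the percentage of trials significant; the t and exact signed-rank tests compare week 6 with 4.

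| Mean CGI-I, week 1 to week 6 | ANOVA | One-sample t | Signed-rank |
|---|---|---|---|
| 4.0 throughout (no change) | 5.2 | 4.6 | 1.9 |
| 2.5 throughout | 5.2 | 99.4 | 98.8 |
| 3.5 to 3.0 | 27.5 | 85.1 | 77.1 |
| 3.5 to 2.5 | 84.3 | 99.4 | 98.8 |
| 4.0 to 3.0 | 84.3 | 84.9 | 75.8 |
| 5.0 to 4.0 | 85.0 | 4.6 | 1.9 |

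The ANOVA gives the same 5.2% for a sustained mean of 2.5 as for no change at all. It gives nearly the same figure for 4.0 to 3.0 (improvement) as for 5.0 to 4.0 (no net improvement).

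**Step 3: range.** Over SD 0.8–1.3 and correlation 0.3–0.8 (4,000 trials per cell):

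- 2.5 throughout: ANOVA 4.6–5.3%, t 94.0–100%.
- 3.5 to 3.0: ANOVA 12.7–58.2%, t 65.9–96.1%.
- 4.0 to 3.0: ANOVA 41.2–99.8%, t 64.8–95.6%; ANOVA minus t runs from −25 to +22 points.

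A separate run used between- and within-patient SDs of 0.7 (total SD √0.98 = 0.99, correlation 0.49/0.98 = 0.5) and n of 8, 10 and 12. For a mean of 2 at every visit, the ANOVA was significant in 4.7–5.1% of trials and the t in at least 99.96%.

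With 25% dropout and LOCF: 2.5 throughout gives ANOVA 4.8%, t 99.6%; 4.0 to 3.0 gives 72.1% and 68.0%.

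**The case against.** The strongest case against has four parts.

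- **The test may not be meant for CGI-I.** The SAP names no scale, so leaving CGI-I unnamed singles nothing out. Its ANOVA is for changes in the psychometric tests. CGI-I already rates change, so the phrase could be confined to the scales with a baseline and CGI-I left to description. The sentence "For each outcome variable, the modified ITT population included all subjects with at least one post-baseline psychometric measurement" defines a population and assigns no test. This stands in part. That sentence does link every outcome variable to a psychometric measurement, and CGI-I is a listed outcome, so the ANOVA is the natural reading. A reader might infer that the wrong test was in fact used on CGI-I; the documents do not establish that.

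- **The ANOVA can pick up improvement.** This stands. A reader might infer that the ANOVA is incapable of responding to improvement on CGI-I. The 3.5-to-2.5 and 4.0-to-3.0 rows contradict that, and at correlation 0.8 the ANOVA leads the t for 4.0 to 3.0 (98.2% against 85.6%). Late onset is plausible, since after the initial dose "Thereafter the dose will be flexible based on response and tolerance". The supportable statement is narrower: a significant F may reflect improvement but does not by itself establish it.

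- **The striking rows are chosen shapes with outside inputs.** This stands for the percentages. A full effect by week 1 and an early worsening are illustrations, not forecasts. The invariance in step 1 depends on none of them.

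- **Little is at stake.** This largely stands. Visit means printed beside the p-value would show level and direction, so misreading requires the p-value to be quoted alone.

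**Conclusion.** The concern holds in a limited, conditional form. CGI-I has no baseline rating, and the only test the SAP gives for rating scales, if applied to CGI-I, is not anchored to no change. That much is algebra. Its size depends on assumed inputs: about 5% of trials significant for a sustained mean of 2.5 (t: 99%), about 85% for 5.0 returning to 4.0 (t: 5%), and about 85% for both tests when improvement runs from 4.0 to 3.0.

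If the ANOVA was not meant for CGI-I, that part of the secondary outcome has no usable stated analysis, and the same one-sentence remedy applies. The point does not reach CGI-S, RAAPP, OAS-M or CAS-P, and it has no bearing on the trial's primary conclusions. It is a low-cost improvement to consider, held with medium confidence.

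**What to change.** For CGI-I only:

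1. As the main result, report the week-6 (LOCF) distribution of ratings and the number and proportion improved, with an exact (Clopper-Pearson) 95% CI. State the cut-off; much or very much improved is one possibility, assumed here because the documents give none. For illustration, 8 of 12 gives 67%, CI 34.9% to 90.1%.
2. If a p-value is wanted, replace the ANOVA with one two-sided signed-rank test of the week-6 rating against the scale's no-change score, and state the direction. Take that score from the rating form and write it down; the value 4 used here is an assumption.
3. Keep the ANOVA for CGI-S and the three primary scales.
4. The SAP is written in the past tense. If the analysis has been run, label the CGI-I result post hoc.

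The cost is one sentence and a rerun on data already collected: no new visits, patients or added p-value. The downsides are these.

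- When improvement begins only after week 1, power can be lost. For 4.0 to 3.0 the signed-rank test gives up 84.3 − 75.8 = 8.5 points at correlation 0.6. It uses week 6 alone, so without dropout its power does not depend on the correlation, and at 0.8 the loss is about 98.2 − 75.8 = 22 points.
- The exact signed-rank test is conservative at n = 12 (1.9% under no change, against 4.6% for the t).
- LOCF carries early ratings forward. With 25% dropout and an extreme course from 5.5 back to 4.0, a week-6 t is significant in 9.7% of trials although the true week-6 change is nil. Stating direction limits the misreading.
- In a single-arm, open-label trial, a significant result shows change from baseline, not a drug effect.

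### A subject who stops before week 6 may have no on-treatment laboratory or ECG value, because the schedule has no early-stop assessment

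*Protocol*

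**What the plan says.** Under Main outcome measures, the protocol states that "initial and endpoint fasting blood sugars and lipids will assess the effect of weight change" and that "An initial and endpoint ECG will be obtained to monitor patients for any changes in the QT-corrected interval". The word endpoint is not defined. For prolactin the text reads "Obtaining serum prolactin levels as well as screening for the sexual dysfunction adverse effects", and for liver function "A gamma-GT will be collected to monitor liver function"; neither sentence gives a time. The text does not mention CBC.

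The Schedule of Events has six columns: screening, baseline, and weeks 1, 2, 4 and 6. All the tests named above are marked at screening and week 6 and nowhere else. The phlebotomy row has the same two marks. There is no early-stop column, and neither document describes a discontinuation visit.

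The SAP provides for early stopping. Its population rule is "For each outcome variable, the modified ITT population included all subjects with at least one post-baseline psychometric measurement". Its missing-data rule begins "In cases where a subject did not complete the entire 6-week trial" and continues that "the last available observation was carried forward (LOCF) and used for statistical comparisons". It also says that "bivariant data were contrasted using paired-t tests". It does not mention laboratory values or the ECG.

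**The concern.** The plan keeps a subject in the analysis after one post-baseline rating, yet the blood tests and ECG have a single on-treatment time point, at the last week. A subject who stops at week 1, 2 or 4 can therefore be analysed for efficacy while having no planned on-drug prolactin, gamma-GT or CBC, and perhaps no glucose, lipid or QTc value either.

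The Rationale gives this some weight. It names weight gain, hyperprolactinemia and extrapyramidal symptoms as the problems with risperidone, and expects adverse effects not to limit aripiprazole. Weight and the movement scales are taken at every visit after baseline; prolactin is the only one of the three with no interim measurement. Subjects who stop early may include those who tolerated the drug poorly, so an abnormality in one of them could go unseen.

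**Working it through.** The documents state no figure on this point that could be reproduced, so the check is mainly a comparison of texts.

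**Inputs.** Planned sample: 12 subjects, single arm, 6 weeks (protocol, Dose and Schedule of Treatment). Visit marks: Schedule of Events. Handling of non-completers: SAP. Dropout rate: not stated.

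**Step 1: schedule against text.**

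| Measure | Marked in schedule | Timing in text | Subject stopping at week 1, 2 or 4 |
|---|---|---|---|
| Prolactin | screening, week 6 | none | no planned on-drug value |
| Gamma-GT | screening, week 6 | none | no planned on-drug value |
| CBC | screening, week 6 | not mentioned | no planned on-drug value |
| Fasting glucose, lipids | screening, week 6 | initial and endpoint | none by the schedule; a value if endpoint means last visit |
| ECG | screening, week 6 | initial and endpoint | none by the schedule; a value if endpoint means last visit |
| Vitals, height, weight, BMI | all six visits | no visit named | captured |
| AIMS, SAS, BAS, UKU | baseline, weeks 1, 2, 4, 6 | no visit named | captured |

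The gap is firm for the first three rows. For glucose, lipids and ECG it depends on an undefined word.

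**Step 2: what the SAP would do with such a subject.** No sentence is tied to laboratory or ECG data. Two could be applied.

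- Paired t-test: it needs both values, so a subject without the second one does not contribute.
- LOCF: the last available value of a test done only at screening is the screening value. Change = screening − screening = 0. A pre-treatment value would be counted as an on-treatment result showing no change.

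Neither supplies an on-drug observation.

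**Step 3: how many subjects.** With d early stoppers and the schedule followed as written, 12 − d subjects have a planned on-drug value: 11, 10, 9 and 8 for d = 1 to 4. For an assumed stopping rate q, acting independently across subjects, the expected number with a value is 12 × (1 − q), and the chance of at least one stopper is 1 − (1 − q)^12:

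| Assumed q | Expected with a value | Chance of at least one stopper |
|---|---|---|
| 10% | 10.8 | 72% |
| 20% | 9.6 | 93% |
| 30% | 8.4 | 99% |
| 40% | 7.2 | >99% |

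The rates are assumptions. The table shows only that the plan is likely to meet the situation at least once, and that with one or two stoppers the number affected is small (1/12 = 8%, 2/12 = 17%).

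**The case against.** The strongest reply is that endpoint can mean the subject's last visit, whenever that falls. The protocol's Previous Work section also uses the word for cited studies without tying it to a fixed week. On that reading, glucose, lipids and ECG are already planned at early stop, and what is missing is a definition. This stands for those tests. It does not reach prolactin, gamma-GT or CBC, for which the documents give no on-treatment time other than week 6. An unscheduled sample at early stop is not forbidden, but it is not planned.

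A second reply is that early stoppers are not lost to safety assessment. This also stands. Weight, vitals, UKU, AIMS, SAS and BAS are recorded from week 1, and the text pairs prolactin with screening for sexual adverse effects. A reader might infer that non-completers disappear from the safety data or that the efficacy results are compromised. The schedule supports neither inference.

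Two further readings go too far:

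- A reader might infer that the SAP carries screening laboratory values forward. It does not say so. The LOCF sentence sits between two sentences about psychometric tests, which suggests that the rating scales were meant. Its wording is not restricted to them, however, so the scope is unclear. That early stoppers drop out through the paired test is likewise an inference, because that sentence is not linked to laboratory data.
- A reader might infer that samples at early stop would restore the precision of the week-6 mean change or remove bias from it. They would not. They reflect shorter exposure. If an early value shows only part of the six-week change, pooling it can pull the mean down even where that subject's six-week change would have been larger than the completers'. The documents give no standard deviation, effect size, safety hypothesis or dropout rate from which a loss of power or a bias could be derived.

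**Conclusion.** The point holds as a minor gap in data collection and safety reporting. It is firm for prolactin, gamma-GT and CBC. For glucose, lipids and ECG it is an undefined endpoint that may or may not leave a gap. How any of these data are analysed is not stated.

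The size is unknown, because the number of early stoppers is unknown; with 1 or 2 of 12 it is small. What can be gained is the chance to see an individual on-drug abnormality in a subject who stopped, and a clear statement of who lacks a value. The conclusion assumes that the schedule is followed as written and that at least one subject stops after starting treatment and before week 6.

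**What to change.** 1. If data collection is still open, add a footnote to the Schedule of Events: for a subject who stops early, the laboratory tests and ECG already planned for week 6 are obtained at the discontinuation visit. Define endpoint to match. This concerns data collection only, not dosing or when treatment stops.
2. State in the SAP that a screening or baseline value is never carried forward as an on-treatment laboratory or ECG value.
3. Report laboratory and ECG changes on observed pairs, giving n, time on drug at the second sample and the number lacking a value. Use week-6 completers for the mean-change summary and list early-stop values separately, mainly to detect individual abnormalities.

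The SAP is written in the past tense. If data collection is complete, only items 2 and 3 apply, and they need no new data.

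The cost is one footnote, a definition and two or three SAP sentences, plus one set of already planned tests per early stopper. The drawbacks are that exposure at sampling will vary and that some stoppers may not return.
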